5.1.2. Part 2 - Atopic Dermatitis Participants

Statistical inference will be made on the secondary endpoint: (percentage change from baseline in EASI score at Week 6). The null hypothesis is that there is no difference between the treatment group and the placebo group. The alternative hypothesis is that the treatment group (PF-07242813 arm) is superior to the placebo group at Week 6. The study will be considered positive, if this null hypothesis is rejected.

The sample size calculation is based on the secondary endpoint (percent change from baseline in EASI score at Week 6). A total of 24 randomized participants with a randomization ratio of 2:1 into the treatment and placebo group will provide approximately 80% power to detect a difference of 50 in percent change from baseline with a common standard deviation 46% between PF-07242813 and the placebo arm with 1-sided alpha=0.05.

Cohort 9 will enroll 24 participants with moderate to severe AD at the MTD.

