5.2.3. Analyses for Continuous Endpoints: Part 2 - Atopic Dermatitis Participants

Landmark (cross-sectional) analysis of key continuous endpoints will use analysis of covariance (ANCOVA). The ANCOVA model will include terms for treatment arm and baseline score of the dependent variable. Least-squares means at the mean overall baseline score will be presented along with 90% confidence intervals.

Mixed model repeated measures (MMRM) models will be used. The fixed effects of treatment, visit (Weeks 1, 2, 3, 4, and 6), and treatment-by-visit interaction will be included. Visit will be modeled as a categorical covariate. Unstructured covariance matrix will be assumed for the model errors. Compound symmetry covariance matrix will be used if the model with unstructured covariance doesn't converge.

When modeling the percentage change from baseline values, the variable for visit will start with the first post-baseline visit, and the actual baseline value will be included as a covariate. At each visit, estimates of least square mean (LSM) values and the LSM differences between the PF-07242813 and the placebo arm will be derived from the model. The corresponding p-values and 90% confidence intervals will also be derived from the model.

Unless stated otherwise, descriptive summary statistics for all continuous variables will be presented on mITT observed data by treatment group and will include the following: n, mean, median, standard deviation, minimum and maximum.

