Appendix 2. Summary of Efficacy Analyses

Efficacy Endpoint	Analysis Type	Population	Data Inclusion and Rules for Handling Intercurrent Events and Missing Data	Analysis Model/Method
Week 6 PCFBL in EASI	Primary Analysis	mITT	MI	ANCOVA
All Visits IGA Response	Secondary Analysis	mITT	NRI	Chan and Zhang (1999) ²
All Visits CFBL PP-NRS Response	Secondary Analysis	mITT	OD	MMRM
All Visits EASI – 75 Response	Secondary Analysis	mITT	NRI	Chan and Zhang (1999) ²
CCI				
	Main analysis	mITT	All data collected will be included regardless of intercurrent events. Missing data will be imputed.	ANCOVA
	CCI			

PCFBL= Percent change from baseline; CFBL= Change from baseline; ANCOVA = Analysis of Covariance; OD = Observed data.

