Appendix 3. Data Derivation Details

Appendix 3.1. Definition and Use of Visit Windows in Reporting

Visit windows will be used for efficacy variables (except change from baseline in pruritus NRS severity and frequency), and for any safety data (except the laboratory data) that display or summarize by study visit. For other endpoints (eg, ECG, vital signs, Physical Exam, Skin tolerability etc.), visit windows will be applied for summary statistics by study visits if required.

Visit No.	Visit Label	Target Day	Visit Window
	Screening	N/A	$-42 \leq \text{day} \leq -1$
1	Baseline*	1	day = 1
2	Week 1	8	$2 \leq \text{day} \leq 11$
3	Week 2	15	$12 \leq \text{day} \leq 22$
4	Week 4	29	$23 \leq \text{day} \leq 36$
5	Week 6	43	$37 \leq \text{day} \leq 50$
6	Week 8	57	$51 \leq \text{day} \leq 71$
7	Week 12	85	$72 \leq \text{day} \leq 99$
8	Week 16	113	day ≥ 100

* Baseline analysis visit window may be considered as day ≤ 1 in some analyses (eg, those involving change from baseline). That is, in case that Day 1 observation is missing, the last observation by the first dosing date may be considered as the baseline. The baseline measurements for demography, height, pre-study medical history and medications will be collected at the “Screening” visit.

If two or more visits fall into the same window, keep the one closest to the Target Day. If two visits are equaled distant from the Target Day in absolute value, the later visit should be used.

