Appendix 3.2. Definition and Use of Visit Windows in pruritus NRS

Visit Label	Target Day	Visit Window
Baseline*	1	day = 1
Day 2	2	day = 2
Day 3	3	day = 3
Day 4	4	day = 4
Day 5	5	day = 5

Day 6	6	day = 6
Day 7	7	day = 7
Day 8	8	day = 8
Day 9	9	day = 9
Day 10	10	day = 10
Day 11	11	day = 11
Day 12	12	day = 12
Day 13	13	day = 13
Day 14	14	day = 14
Week 2	15	$15 \leq \text{day} \leq 22$
Week 4	29	$23 \leq \text{day} \leq 36$
Week 6	43	$37 \leq \text{day} \leq 50$
Week 8	57	$51 \leq \text{day} \leq 71$
Week 12	85	$72 \leq \text{day} \leq 99$
Week 16	113	$\text{day} \geq 100$

* Baseline analysis visit window may be considered as day ≤ 1 in some analyses (eg, those involving change from baseline). That is, in case that Day 1 observation is missing, the last observation by the first dosing date may be considered as the baseline. The baseline measurements for demography, height, pre-study medical history and medications will be collected at the “Screening” visit.

If two or more visits fall into the same window (only for Weeks 2, 4, 6, 8, 12, 16), keep the one closest to the Target Day. If two visits are equaled distant from the Target Day in absolute value, the later visit will be used.

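### If the unstructured MMRM fails, the SAP's only fallback is compound symmetry, which miscalibrates the by-visit p-values and 90% intervals whenever the visit variances differ

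*SAP*

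**What the plan says.** SAP 5.2.3 describes the repeated-measures model for continuous endpoints in Part 2. Its fixed effects are treatment, "visit (Weeks 1, 2, 3, 4, and 6") and their interaction. The first-choice covariance is stated as "Unstructured covariance matrix will be assumed for the model errors", and the only alternative as "Compound symmetry covariance matrix will be used if the model with unstructured covariance" does not converge. The model is used for inference: "The corresponding p-values and 90% confidence intervals will also be derived from the model".

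SAP Appendix 2 assigns the row "All Visits CFBL PP-NRS Response" to MMRM on observed data and labels it a secondary analysis. SAP 3.2.3 lists change in pruritus NRS among the tertiary/exploratory endpoints. SAP 5.2.3 also describes the model for percentage change from baseline.

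SAP Appendix 3.2, "Definition and Use of Visit Windows in pruritus NRS", defines Days 2 to 14 singly and then Weeks 2, 4, 6, 8, 12 and 16.

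The Week 6 EASI comparison is specified elsewhere. SAP 6.2.1.1 and Appendix 2 give it an ANCOVA after multiple imputation.

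**The concern.** Compound symmetry estimates one variance and one correlation for all visits. A visit whose true variance is above the average gets a standard error that is too small, and a visit below the average gets one that is too large.

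For a change score adjusted for baseline, the residual variance at a visit is proportional to 1 − ρ², where ρ is that visit's correlation with baseline. If ρ falls with time, which is the usual expectation, the variance rises and Week 6 is the visit with the understated standard error.

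Structures that keep a separate variance for each visit, with far fewer parameters than the unstructured matrix, lie between the two named options. The readable text tries none of them. Naming them in advance would also avoid choosing a covariance after seeing the data in a sponsor-open study.

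**Working it through.** **Inputs.** From SAP 5.1.2: "A total of 24 randomized participants with a randomization ratio of 2:1 into the treatment and placebo group", so 16 and 8; difference 50; SD 46; one-sided alpha 0.05. From SAP 5.2.3: five visits and 90% intervals. SDs by visit are not in the documents, so every profile below is an assumption. Only the shape of a profile matters, so the results are not specific to EASI or NRS units.

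**1. The plan's own figure.** SE = 46 × √(1/8 + 1/16) = 19.92. Power = Φ(50/19.92 − 1.645) = Φ(0.865) = 0.807, or 0.784 from the noncentral t with 22 df. The stated 80% or so is reproduced. This confirms the inputs; it is not itself in question.

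**2. Formula.** With complete data and separate treatment means at each visit, the estimated difference at Week 6 is the same under either structure. Only its standard error changes. The compound-symmetry variance is the mean of the visit variances, so

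SE ratio at visit j = √(mean of SD² over visits) / SD at visit j.

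Example, SD rising evenly from 23 to 46: the SDs are 23, 28.75, 34.5, 40.25 and 46. The mean of their squares is 6281.875/5 = 1256.4, and its root is 35.4. The Week 6 ratio is 35.4/46 = 0.77; the first-visit ratio is 35.4/23 = 1.54. Large-sample coverage of a 90% interval at Week 6 is 2Φ(1.645 × 0.771) − 1 ≈ 0.795.

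**3. Simulation.** 40,000 null trials per profile, 16 vs 8, five visits, compound-symmetry REML with Satterthwaite df, no baseline covariate, no missing data.

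| Assumed SD profile to Week 6 | SE ratio at Week 6 | 90% interval coverage | One-sided error |
|---|---|---|---|
| 23 rising to 46 | 0.77 | 80% | 0.10 |
| 35 rising to 46 | 0.88 | 86% | 0.07 |
| flat at 46 | 1.00 | 90% | 0.05 |
| 35, 50, 55, 52, 46 | 1.05 | 91% | 0.04 |
| 60 falling to 46 | 1.16 | 94% | 0.03 |

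The unstructured model covered 90% in every row. Correlation of 0.5 or 0.7 (exchangeable), or 0.7 with AR(1) decay, made almost no difference. Nor did four visits instead of five, checked for the 23-to-46 profile.

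**4. Profiles set by correlation with baseline.** Weeks 1, 2, 4 and 6, with ρ falling linearly in weeks to 0.5 at Week 6 and residual variance 1 − ρ². Starting at 0.9, ρ is 0.9, 0.82, 0.66, 0.5; the variances are 0.190, 0.328, 0.564, 0.750, with mean 0.458. The Week 6 ratio is √(0.458/0.750) = 0.78; the first-visit ratio is √(0.458/0.190) = 1.55. Errors and coverage come from 20,000 simulated null trials per row.

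| ρ at Week 1 | SE ratio at Week 6 | Coverage | One-sided error |
|---|---|---|---|
| 0.9 | 0.78 | 80% | 9.8% |
| 0.8 | 0.85 | 84% | 8.3% |
| 0.7 | 0.91 | 87% | 6.5% |

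**5. How likely is the fallback?** An unstructured matrix for T visits has T(T+1)/2 parameters.
- Five visits (5.2.3): 5 × 6/2 = 15. Four visits (Weeks 1, 2, 4 and 6, as windowed in Appendix 3.1): 4 × 5/2 = 10.
- Nineteen time points (Appendix 3.2: 13 days plus 6 weeks): 19 × 20/2 = 190, from 24 participants.

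In 240 simulated trials with four or five visits, 10% or 25% monotone dropout and one assumed rising variance profile, the unstructured REML fit converged every time. That check was not run in SAS.

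**The case against.** Three stronger readings are tempting, and the documents do not support them.

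- **The 5% level of the decisive Week 6 test is lost.** A reader might infer this because 5.2.3 speaks of percentage change and SAP 5.1.2 sets a one-sided 5% level. But SAP 5.1.2 attaches the formal hypothesis to Week 6 EASI alone, and SAP 6.2.1.1 analyses that by ANCOVA with multiple imputation, which uses no repeated-measures covariance.
- **Week 6 intervals will be too narrow.** This holds only if Week 6 variance exceeds the average over visits. The documents give no SD by visit; the 46 is a common SD for the two arms at Week 6. Over the assumed profiles the ratio runs from 0.77 to 1.16, so the direction can reverse.
- **The fallback will probably be used because 190 parameters are needed.** SAP 5.2.3 lists five visits, and Appendix 3.2 is a table of reporting windows, not a model statement. The 190 applies only if all of those windows enter the analysis that Appendix 2 describes as covering all visits. With 10 or 15 parameters, failure is possible but not shown to be likely.

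Two further cautions stand. SAP Appendix 7 (the MMRM appendix) and the NRS detail added in 6.2.2 cannot be read in the public copy, so a df rule or a separate diary analysis may be there; neither can be called missing. The heterogeneous structures proposed below were not simulated; what was shown to hold 90% coverage is a variance estimated separately for each visit.

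What survives is narrow: the stated rule moves from the most flexible structure to one that forces equal variances, and by-visit inference is taken from whichever is fitted.

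**Conclusion.** The point holds conditionally. If the unstructured model does not converge and visit variances differ, the by-visit p-values and 90% intervals from the SAP's MMRM are miscalibrated. Under the assumed growing variance, Week 6 coverage is about 80% to 87% and one-sided error about 6.5% to 10%. The first visit's standard error is up to about 55% too large. If Week 6 variance is below average, its intervals are too wide, with coverage up to about 94%.

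The figures rest on assumed variance profiles, complete data and a 16:8 split. The reach is limited to MMRM results, visibly the exploratory change in pruritus NRS and any MMRM of percent change. The main EASI conclusion is unaffected. The fallback is a more serious prospect if the 19 NRS time points are modelled together than with the five listed visits. This is a cheap improvement, not a threat to the study's main result.

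**What to change.** In SAP 5.2.3, replace the single fallback with an ordered list of structures that let variance differ by visit, using Kenward-Roger degrees of freedom throughout:

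1. Heterogeneous Toeplitz (five visits: 5 variances + 4 correlations = 9 parameters, against 15 unstructured).
2. ARH(1) (5 + 1 = 6).
3. Heterogeneous compound symmetry (5 + 1 = 6).
4. Plain compound symmetry (2) only as a last resort.

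Do not rely on sandwich standard errors to repair plain compound symmetry; with 8 placebo participants they are doubtful themselves.

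State which visits enter the NRS model, and keep the daily diary days out of the weekly-visit MMRM. While doing so, reconcile the visit list. SAP 5.2.3 includes Week 3, the window table under "Visit windows will be used for efficacy variables" (Appendix 3.1) has none, and the protocol's Table 3 labels Day 8 as Week 2 and Day 15 as Week 3.

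The cost is a few sentences in the SAP and a few lines of code. The downside is a slightly longer model-fitting sequence.

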5.2.4. Analyses for Categorical Endpoints: Part 2 - Atopic Dermatitis Participants

NA.

5.2.5. Analyses for Time-to-Event Endpoints: Part 2 – Atopic Dermatitis Participants

NA.

5.3. Methods to Manage Missing Data

5.3.1. PK Data

5.3.1.1. Concentrations Below the Limit of Quantification

In all data presentations (except listings), concentrations below the limit of quantification (BLQ) will be set to zero. (In listings BLQ values will be reported as “<LLQ”, where LLQ will be replaced with the value for the lower limit of quantification).

5.3.1.2. Deviations, Missing Concentrations and Anomalous Values

In summary tables and plots of median profiles, statistics will be calculated having set concentrations to missing if any of the following cases is true:

- A concentration has been collected as ND (ie, not done) or NS (ie, no sample);
- A deviation in sampling time is of sufficient concern or a concentration has been flagged anomalous by the pharmacokineticist.

Note that summary statistics will not be presented at a particular time point if more than 50% of the data are missing.

5.3.1.3. Pharmacokinetic Parameters

Actual PK sampling times will be used in the derivation of PK parameters. If a PK parameter cannot be derived from a participant’s concentration data, the parameter will be coded as NC (ie, not calculated). (Note that NC values will not be generated beyond the day that a participant discontinues).

In summary tables, statistics will be calculated by setting NC values to missing; and statistics will be presented for a particular dose level with ≥ 3 evaluable measurements.

If an individual participant has a known biased estimate of a PK parameter (due for example to an unexpected event), this will be footnoted in summary tables and will not be included in the calculation of summary statistics or statistical analyses.

5.3.2. Efficacy Data

The following patient level data descriptions are also required for defining the pre-specified analyses:

Defined Analysis Data set (at the data level) – endpoint specific	Description
Primary Estimand Continuous Endpoint Set	
This set will include all patients in the mITT population. All data for a subject after the initiation of prohibited medications will be set to missing.
 
Note the primary estimand requires multiple imputation which will be performed on this dataset, the multiple imputations themselves will not be saved in the database, however, the SAS specifications and random number seed will be.

Secondary Estimand Categorical Endpoint Set	
This set will include all patients in the mITT population. All data for a subject after the initiation of prohibited medications, withdrawal of either study drug or the study itself will be set to a failure. Any other additional missing data will be recorded as a failure. Subjects will have either a success or failure in the dataset for all scheduled visits.

Observed Efficacy Set	
This set will include all patients in the mITT population and all observed data and includes all data recorded from the CRF pages. No data will be set to missing or modified from the original CRF record.

The primary analysis will use the primary estimand continuous endpoint set. For each landmark analysis (eg, Cross sectional analysis by week) missing data will be imputed using a control-based imputation method. PROC MI will first be called at the visit and a control-based method (implemented with the missing not at random (MNAR) option) will impute missing vehicle observations under the assumption data are missing at random (MAR) and impute missing treatment observations assuming they are similar to corresponding vehicle patients. Imputation will use the full conditional specification (FCS) method, the imputed data for the treatment and placebo arms will be combined for the analysis.

Summaries of continuous data will use the observed data only and no additional considerations are needed.

Analysis of binary data will use the Secondary Estimand Categorical Endpoint Set. This dataset by definition has no missing data since all missing values will have been set to a failure. Summaries will use the Observed Efficacy Set and will report results on an observed case (OC) basis.

6. ANALYSES AND SUMMARIES

6.1. Part 1: Healthy Adult Participants

6.1.1. Primary Endpoint(s)

6.1.1.1. Safety Summaries and Analyses

All safety analyses will be performed on the safety population.

All safety data will be summarized descriptively through appropriate data tabulations, descriptive statistics, categorical summaries, and graphical presentations. Change from baseline on laboratory data and vital signs will be additionally summarized. Participant listings will also be produced for these safety endpoints.

6.1.1.1.1. Adverse Events

An adverse event is considered a Treatment-Emergent Adverse Event (TEAE) if the event started during the effective duration of treatment. All events that start on or after the first dosing day and time/start time, if collected, but before the last dose plus the lag time will be flagged as TEAEs. The algorithm will not consider any events that started prior to the first dose date. Events that occur in a non-treatment period (follow-up or washout period) will be counted as treatment emergent and attributed to the previous treatment taken.

6.1.1.1.2. Laboratory Data

Safety laboratory tests will be performed as described in the protocol. To determine if there are any clinically significant laboratory abnormalities, the hematological, clinical chemistry (serum) and urinalysis safety tests will be assessed against the criteria specified in the sponsor reporting standards. The assessment will take into account whether each participant's baseline test result is within or outside the laboratory reference range for the particular laboratory parameter. Baseline of safety laboratory tests will be the last pre-dose measurement.

6.1.1.1.3. Vital Signs

Single supine blood pressure (both diastolic and systolic), pulse rate, respiratory rate and/or temperature will be collected at times specified in the Schedule of Activities in the protocol.

The following vital signs endpoints will be determined and summarized for each treatment group.

- Actual values, change from baseline in supine blood pressure, pulse rate, respiratory rate and temperature over all measurements taken postdose;
- The maximum decrease and increase from baseline over all measurements taken postdose for supine blood pressure.

Baseline will be defined as the last pre-dose recording. The increase from baseline will be calculated by subtracting the baseline value from each post-dose measurement to give the change from baseline for each participant. The maximum of these values over the duration of dosing will be reported as maximum increase from baseline, except where a participant does not show an increase. In such an instance, the minimum decrease will be reported.

Similarly, decrease from baseline will be calculated by subtracting each post-dose measurement from individual participant's baseline value. Maximum decrease from baseline will be reported as the minimum value of the changes from baseline. In cases where a participant does not show a decrease, the minimum increase will be reported.

Maximum absolute values and changes from baseline for vital signs will also be tabulated by treatment using categories as defined in [Appendix 1](#).

6.1.1.1.4. ECG

The QT, QTc, PR, heart rate (HR) and QRS complex will be recorded at each assessment time, as specified in the Schedule of Activities.

If not supplied, QTcF will be derived using Fridericia's heart rate correction formula:

$$QTcF = \frac{QT}{(RR)^{1/3}} \quad \text{where } RR = 60/\text{HR}(\text{if not provided}).$$

The average of the triplicate ECG measurements collected before dose administration on Day 1 of each cohort will serve as each participant's baseline value.

Changes from baseline for the ECG parameters QT interval, heart rate, QTc interval, PR interval, and QRS complex will be summarized by treatment and time.

Changes from baseline will be defined as the change between postdose ECG parameter values and the baseline. If triplicate postdose measurements are collected, the average of the values will be used in the analysis.

The maximum absolute value (post-dose) and the maximum increase from baseline for QTcF, QT, heart rate, PR and QRS, will be determined over all measurements taken post-dose and reported.

The number (%) of participants with maximum postdose QTc values and maximum increases from baseline in the following categories will be tabulated by treatment:

Safety QTc Assessment

Degree of Prolongation	Mild (msec)	Moderate (msec)	Severe (msec)
Absolute value	$>450\text{-}480$	$>480\text{-}500$	>500
Increase from baseline		30-60	≥ 60

In addition, the number of participants with uncorrected QT values >500 msec will be summarized.

If more than 1 ECG is collected at a nominal time after dose administration (for example, triplicate ECGs), the mean of the replicate measurements will be used to represent a single observation at that time point. If any of the 3 individual ECG tracings has a QTc value >500 msec, but the mean of the triplicates is not >500 msec, the data from the participant's individual tracing will be described in a safety section of the CSR in order to place the >500 -msec value in appropriate clinical context. However, values from individual tracings within triplicate measurements that are >500 msec will not be included in the categorical analysis unless the average from the triplicate measurements is also >500 msec. Changes from baseline will be defined as the change between the postdose QTc value and the average of the time-matched baseline triplicate values on Day -1, or the average of the predose triplicate values on Day 1.

In addition, an attempt will be made to explore and characterize the relationship between serum concentration and QT interval length using a PK/PD modeling approach. If a PK/PD relationship is found, the impact of participant factors (covariates) on the relationship will be examined.

In addition, PR and QRS maximum values and maximum increases from baseline will also be tabulated by treatment using categories as defined in [Appendix 1](#).

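### The exploratory concentration-QT model in SAP 6.1.1.1.4 names the QT interval as its response; change from baseline in QTcF should be named instead

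*SAP*

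**What the plan says.** The model appears in one sentence of SAP 6.1.1.1.4 (ECG, Part 1), whose stated aim is to "characterize the relationship between serum concentration and QT interval length using a PK/PD modeling approach". It is worded as an exploratory step: "an attempt will be made to explore and characterize the relationship". A further sentence then deals with covariates: "If a PK/PD relationship is found, the impact of participant factors (covariates) on the relationship will be examined". No equation, baseline term, placebo handling, heart-rate term, threshold or decision rule is given.

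Elsewhere the section keeps QT and QTc apart:

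- It summarises by treatment and time "Changes from baseline for the ECG parameters QT interval, heart rate, QTc interval, PR interval, and QRS complex".
- It plans a separate count, in which "the number of participants with uncorrected QT values >500 msec will be summarized".
- It supplies the corrected variable: "If not supplied, QTcF will be derived using Fridericia's heart rate correction formula", that is QTcF = QT / RR^(1/3) with RR = 60/HR.
- Its mild, moderate and severe prolongation categories are defined on QTc. SAP Appendix 1 categorises increase from baseline in QTcF.

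The section gives two baselines. The first is the mean of the Day 1 predose triplicate. Later it states: "Changes from baseline will be defined as the change between the postdose QTc value and the average of the time-matched baseline triplicate values". Those readings are placed on Day -1, and the Day 1 predose mean is offered as the alternative.

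**The concern.** The uncorrected QT interval shortens as heart rate rises and lengthens as it falls, with no change in repolarisation. If heart rate varies with concentration, a slope fitted to QT carries both effects. A flat slope could then hide a true effect, and a positive slope could reflect slowing of the heart alone. The covariate step does not protect against the first case, because it is taken only once a relationship has been found.

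There is a plausible route for such confounding in the IV cohorts. Protocol 7.1.1 describes infusion reactions with symptoms such as chills and fever. Protocol 2.2.1.2 notes a potential for cytokine release, and the schedules of activities for the SAD cohorts and for Cohort 9 take cytokine samples around the infusion. Protocol Table 5 projects Tmax at 1 hour for the 1000 mg IV regimen, the end of a 1-hour infusion. Heart rate and concentration could therefore be high together.

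The choice also departs from the rest of the plan. Protocol 7.1 sets its ECG discontinuation criteria on QTcF and QTc. Exclusion criterion 24 in Protocol 5.2 requires a long uncorrected QT to be Fridericia-corrected before it is used.

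**Working it through.** The documents give no sample size, power, threshold or expected slope for this model, so there is no figure to reproduce. The check is how far QT moves with heart rate under the SAP's own formula.

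**Inputs**

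- From SAP 6.1.1.1.4: QTcF = QT / RR^(1/3) and RR = 60/HR, so QT = QTcF × (60/HR)^(1/3).
- Assumed, not in the documents: QTcF 400 ms (range 380 to 420), baseline HR 55 to 70 bpm, and a 10 ms shift as the yardstick.

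**Heart-rate rise that cancels a true +10 ms in QTcF.** QT is unchanged when 410 × (60/HR1)^(1/3) = 400 × (60/HR0)^(1/3), which gives HR1 = HR0 × (410/400)^3 = HR0 × 1.0769. From 60 bpm, HR1 = 64.6 bpm.

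**Heart-rate fall that creates +10 ms in QT with QTcF fixed at 400.** With QT0 = 400 × (60/HR0)^(1/3), HR1 = 60 / ((QT0 + 10)/400)^3. From 60 bpm, QT0 = 400 ms and HR1 = 60 / (410/400)^3 = 55.7 bpm.

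| Baseline HR (bpm) | Rise that hides +10 ms QTcF (bpm) | Fall that mimics +10 ms QT (bpm) |
|---|---|---|
| 55 | 4.2 | 3.8 |
| 60 | 4.6 | 4.3 |
| 65 | 5.0 | 4.8 |
| 70 | 5.4 | 5.3 |

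**Range over the other assumption.** With QTcF 380 to 420 ms and baseline HR 55 to 70 bpm, a 5 bpm rise moves QT by -8.2 to -12.4 ms, and a 5 bpm fall by +9.0 to +14.0 ms.

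**A larger shift.** At QTcF 400 ms, HR 60 to 70 bpm gives QT = 400 × (60/70)^(1/3) = 380.0 ms. If QTcF also rises to 420 ms, QT = 420 × (60/70)^(1/3) = 399.0 ms, almost the starting 400 ms.

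**With the response changed.** If the Fridericia relation holds exactly, a pure heart-rate shift produces 0 ms change in QTcF, so this route into the slope is removed.

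**The case against.** The strongest reply is that the sentence is loose wording in an exploratory plan. It promises only an attempt and specifies no model, and where the SAP clearly means the raw interval it writes uncorrected QT, a word missing here. That reading is possible. But the section lists QT and QTc as separate parameters and nowhere says that this model uses QTc. If the wording is only loose, the same edit settles it.

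Three stronger readings are tempting, and the documents do not support them:

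- **That the SAP specifies a model with no baseline or placebo term.** It is silent on both, and silence is not a specification. Protocol 9.4.2.1 ends in a redaction and the text of SAP 6.3.5 is not visible, so neither can be counted for or against.
- **That a QT effect would be missed.** Changes in QT, heart rate and QTc are summarised by treatment and time, maximum QTcF and heart rate are reported, and QTc categories are tabulated. An effect on either would have a planned place to show.
- **That the drug alters heart rate, or that dosing decisions rest on this slope.** No heart-rate effect is reported. Protocol 2.2.1.2 records no test article-related effects in the 13-week monkey study, and Protocol 4.2.1 calls the potential for cytokine release syndrome low. The escalation rules in Protocol 6.6.1 do not use the model.

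The confounding route is also limited. Projected Tmax for the SC cohorts is 96 hours (Protocol Table 5), the predicted half-life is 17 days (Protocol 4.3.1), and SAD ECGs run to Day 71. Many concentration-ECG pairs therefore lie far from an infusion, although the end-of-infusion IV points carry the highest concentrations.

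What remains is that the named response is the less suitable of two variables the section already provides.

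**Conclusion.** The point holds at minor severity. Read in the SAP's own terms, the concentration-QT model takes the uncorrected interval as its response, and its slope would then be open to confounding by heart rate. About 4 to 5 bpm is enough to cancel or create 10 ms. That size rests on an assumed QTcF of 400 ms, an assumed baseline of 55 to 70 bpm and an exact Fridericia relation. It measures sensitivity to heart rate, not how likely such a shift is in this trial. The by-treatment ECG summaries and all decision rules are untouched. Only the interpretation of one exploratory slope is affected.

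**What to change.** In the PK/PD sentence of SAP 6.1.1.1.4, replace QT interval length with change from baseline in QTcF, using the mean of triplicates where they are collected and the single reading otherwise. State one baseline for this analysis and reconcile the two definitions in the section. Protocol 8.2.3 already defines baseline QTc as the Day 1 predose triplicate mean. Add a check of heart rate against concentration, so that any rate effect is seen alongside the slope.

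Optionally, include placebo participants at concentration 0. Protocol 9.2.1 plans 16 in the SAD cohorts and up to 10 in the MAD cohorts. The SAP does not say which analysis set feeds the model, and its PK concentration set requires a dose of PF-07242813, so their inclusion would need to be stated.

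The cost is one SAP sentence and slight extra analysis. QT, heart rate and concentrations are already collected, QTcF is already supplied or derived, and no protocol change is needed.
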